1.1 Sample size calculation

For the time to event outcome, use the median reoccurrence time of similar populations in the literature to estimate the hazard ratio (HR). The median reoccurrence time described in the literature is 18 months. If we do not want to miss the 6-month improvement in event time in the treatment group, then HR estimates the risk ratio of reoccurrence time at 18 months in the control group and 24 months in the treatment group.

Risk ratio=(risk rate of treatment group)/(risk rate of control group)

Risk rate=1/(median recurrence time)

Therefore, the risk ratio can be estimated as: Risk ratio=(1/24)/(1/18)=18/24=0.75

The estimated risk ratio is 0.75, which represents a 25% reduction in risk effect for the treatment group compared to the control group. The sample size is based on the parallel design of the superiority program, survival endpoint, 90% efficacy, 0.05 significance level, bilateral significance level, HR 0.75. Using PASS11 software, it is estimated that each group requires 635 cases, and an increase of 10% would result in 700 cases per group. Therefore, the planned total sample size is 1400 patients with lung cancer.

2、 Case selection

In this experiment, qualified participants will be recruited from each center, as the annual number of lung surgeries in each center reaches around 8000 cases.

Inclusion Criteria

1. Age range: 18-80 years old.
2. Electively undergo minimally invasive (thoracoscopic or robotic) surgery for clinical stage I and II lung cancer.
3. Willing and capable of providing consent.

Exclusion criteria

1. Palliative surgery without intention of cure.

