5. Postoperative analgesia management

To reduce the possibility of confounding factors, general

anesthesia should be maintained under a combination of intravenous and inhalation anesthesia. Postoperative care follows the unit's standard to enhance postoperative rehabilitation protocol. The pain control program will be consistent with the unit's standard procedure. However, during IMP infusion, simultaneous continuous infusion of other local anesthetic drugs (such as epidural or wound catheters) cannot be performed. After the surgery, all patients were uniformly treated with sufentanil 2ug/kg diluted to 100ml and pumped with 2ml/h for intravenous analgesia

6. Randomization

After obtaining consent, participants will be randomly assigned (1:1) to receive intravenous lidocaine or placebo using a minimization algorithm. The minimum criteria include age (<45 years, 45-65 years, 65-80 years), gender, trial center.

6. Observation project

Main outcome measure

Assess the reoccurrence time of lung cancer patients within 36 months from the date of surgery.

Secondary outcome measure

1. Disease free survival (DFS)
2. Objective remission rate of patients' diseases
3. Health related Quality of Life Questionnaire EQ-5D-5L
4. Cancer specific quality of life measured using the Functional

Assessment of Cancer Therapy (FACT-L) questionnaire.

Other observation indicators

1. The total length of hospital stay, including readmission, is 36 months.
2. Changes in pro-inflammatory cytokine levels (IL-6, TNG - α) from baseline on the third day after treatment and upon discharge.

On the 1st and 3rd day after treatment and at discharge, changes in reticular fiber dissolution markers (matrix metalloproteinases MMP-9, MMP-2) from baseline were observed.

3. Perioperative nausea, vomiting, delirium, pain control, and incidence of cardiovascular accidents 6 and 12 months after treatment completion.

7. Efficacy evaluation criteria

Follow up chest CT scans at 6, 12, 18, 24, and 36 months after surgery were conducted to evaluate whether lung cancer patients had cancer reoccurrence and the time of reoccurrence within 36 months from the date of surgery. And evaluate the cancer specific quality of life using the lung cancer treatment function assessment questionnaire for patients. The shortened recurrence time and improved specific quality of life indicate therapeutic efficacy.

8. Observation of adverse events

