Statistics will be recorded and managed using Redcap data, and analyzed using SPSS21 software. The analysis will be conducted according to the intention to treat principle. The statistical analysis plan for this study includes summarizing baseline data, conducting primary outcome analysis using time to event analysis, and conducting additional survival analysis. Baseline variables such as age group, gender, comorbidities, ASA classification, cancer stage, cancer TNM classification, pathological type, neoadjuvant targeted therapy, radiotherapy, and chemotherapy will be summarized using appropriate descriptive statistical methods, using mean and standard deviation or median and quartile range (depending on the applicability of continuous variables). The categorical variables will be summarized using the frequency and percentage of participants in each category. Researchers will use EDC to fill out CRF. The data will be stored on a secure server.

The source documents of CRF report information will be archived in the center and available for monitoring, IRB/IEC review, and regulatory inspection as needed. According to applicable regulations, researchers must retain all research records/documents.

The main outcome is defined as the time of cancer reoccurrence within 36 months after surgery in patients with stage I and II lung cancer. Multiple Cox regression models will be used to analyze the main results and adjust the truncated data. The truncated data includes participants who have not experienced recurrence or death within 36 months, as well as those who have been lost to follow-up or withdrawn from the study.

The risk ratio will be estimated by comparing the risk rates of the placebo group and the lidocaine group, taking into account the truncated data of the participants and adjusting for covariates. In addition, Kaplan Meier plots will be used to visualize and compare survival distributions, while Log rank tests will evaluate the differences between the two groups.

We will use the study drug allocation ($x=0$ placebo, $x=1$ lidocaine) as the independent variable, the time of cancer recurrence or death as the dependent variable, and age group (<45, 45-65, 65-80), gender, number of comorbidities, ASA classification, cancer staging, neoadjuvant radiotherapy, and chemotherapy as adjusted covariates.

Clean the experimental data and construct an analysis dataset suitable for statistical analysis. Data quality control is achieved through the accuracy

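### Allocation is minimised on trial centre, but the primary Cox model leaves centre out; if centres differ, the test is conservative and loses a little power

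*Protocol*

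**What the plan says.** Protocol section 6 (Randomization) says that "participants will be randomly assigned (1:1) to receive intravenous lidocaine or placebo using a minimization algorithm". It then names the factors: "The minimum criteria include age (<45 years, 45-65 years, 65-80 years), gender, trial center".

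Section 10 (Statistics process) sets the primary analysis: "Multiple Cox regression models will be used to analyze the main results and adjust the truncated data". Treatment allocation is the independent variable, with "age group (<45, 45-65, 65-80), gender, number of comorbidities, ASA classification, cancer staging, neoadjuvant radiotherapy, and chemotherapy as adjusted covariates". Centre is not in that list. Nowhere does the protocol mention strata by centre, a centre covariate or a centre frailty term. The supporting comparison is described only as "Log rank tests will evaluate the differences between the two groups".

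The design inputs in section 1.1 are "90% efficacy, 0.05 significance level, bilateral significance level, HR 0.75", with medians of 18 and 24 months. The total is 1400 patients, and the main outcome runs to 36 months from surgery.

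**The concern.** Minimising on centre makes the arms nearly equal in size within each centre, which removes most of the chance imbalance between arms in centre mix. A model without centre computes its standard error as if that imbalance could still occur. If centres differ in hazard after the listed covariates are taken into account, two things follow:

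- The standard error is too large for the design, so the nominal 5% test rejects less often than 5% under the null and power is given up.
- The estimated hazard ratio lies nearer 1 than the within-centre ratio. Part of this is non-collapsibility: the hazard ratio averaged over centres is a different quantity, so the shift is not simply bias.

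The protocol chose to balance on centre and then does not use that balance in the analysis. The covariate list is written out in full, so this is a stated choice rather than a detail left open.

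**Working it through.** **1. The lists side by side.** Minimisation uses age group, gender and centre. The Cox model uses age group, gender, number of comorbidities, ASA class, stage, neoadjuvant radiotherapy and chemotherapy. Centre is the only allocation factor missing.

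**2. The protocol's own figures.** HR = (1/24)/(1/18) = 0.75, as stated. Events for 90% power at two-sided 0.05: 4 × (1.960 + 1.282)² / (ln 0.75)² = 508. The stated 635 per group would match 508 events if 508/1270 = 40% of patients had an event. The protocol does not give that proportion, and the present point does not depend on it.

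With 36 months of follow-up for everyone, the event probabilities are 1 − 2^(−36/18) = 0.750 and 1 − 2^(−36/24) = 0.646, so about 978 events in 1400 patients. Adding covariate and centre differences in the simulation brings this to about 940 to 960.

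**3. Assumptions, because the protocol gives no figure.**
- 10 equal centres.
- Normal centre effects with residual SD of the log hazard 0, 0.3 or 0.5. The hazard range across the central 95% of centres is exp(2 × 1.96 × SD), about 1-, 3- and 7-fold.
- Minimisation probability 0.8 and exponential event times.
- Log hazard ratios of 0.2 per age band, 0.2 for gender and 0.7 for stage.

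With constant hazards within centres, medians of 18 and 24 months correspond to a within-centre HR of 0.75 at every SD.

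**4. Simulation.** 1400 patients and 20,000 replicates per cell. The Cox model has arm, age group, gender and stage, fitted without and then with centre strata (two-sided Wald test at 0.05). Scenario A: 36 months at the 18-month control median. Scenario B: 36 months with the hazard lowered by assumption so that 508 events occur.

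| Scenario, SD | Power without centre / stratified | Loss (points) | Mean HR without / stratified | Type I error without / stratified |
|---|---|---|---|---|
| A, 0 | 99.3% / 99.3% | 0.0 | 0.750 / 0.750 | 5.1% / 5.2% |
| A, 0.3 | 99.2% / 99.4% | 0.2 | 0.757 / 0.749 | 4.3% / 4.8% |
| A, 0.5 | 98.2% / 99.1% | 0.9 | 0.769 / 0.749 | 3.9% / 5.5% |
| B, 0 | 90.0% / 89.9% | −0.1 | 0.749 / 0.749 | 5.1% / 5.1% |
| B, 0.3 | 88.7% / 89.5% | 0.8 | 0.754 / 0.750 | 5.0% / 5.4% |
| B, 0.5 | 87.0% / 89.3% | 2.3 | 0.760 / 0.749 | 4.1% / 5.0% |

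Monte Carlo standard error is about 0.15 points for type I error and 0.03 to 0.13 points for the paired power differences.

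**5. Mechanism.** Under the null in scenario A without centre, the mean model standard error at SD 0/0.3/0.5 is 0.0624/0.0628/0.0634, against an empirical SD of 0.0628/0.0610/0.0602. It is right at SD 0, 3% too large at 0.3 (0.0628/0.0610 = 1.03) and 5% too large at 0.5 (0.0634/0.0602 = 1.05). Stratified, the pairs are 0.0626/0.0631/0.0637 and 0.0630/0.0629/0.0646. Stratified type I error averages 5.1% over 18 null settings (4.8 to 5.5%), so little of the power difference reflects test size.

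**6. Sensitivity.** Loss in points at SD 0.3/0.5:

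| Setting | A | B |
|---|---|---|
| HR averaged over centres set to 0.75 | 0.2/0.4 | 0.7/1.8 |
| 3 equal centres | 0.2/0.9 | 0.4/1.6 |
| 10 unequal centres (420 down to 20 patients) | 0.4/0.7 | 0.6/1.7 |

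For the unequal and 3-centre layouts (10,000 replicates), the Monte Carlo standard error of the differences is up to 0.21 points.

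**7. A second simulation with other settings** (1270 patients, 5 or 10 centres, about 500 to 550 events at HR 0.75, 8000 replicates, age and gender as covariates) gave losses of about 1 point at SD 0.3 and 2.4 points at SD 0.5. Type I error without centre was 4.8 to 4.9% and 4.2 to 4.4%. At SD 0.8, an extreme value, the loss was about 7 points (84.8% against 91.6%) and type I error 3.0%.

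**The case against.** **The loss is small and depends on assumptions.** This stands. The protocol gives neither the number of centres nor their spread, and an SD of 0.5 means a roughly 7-fold hazard range after adjustment for stage, ASA class and comorbidities. The protocol describes uniform training, and says of its sites that "the annual number of lung surgeries in each center reaches around 8000 cases", so such a spread may not arise. At SD 0 there is no loss. At SD 0.3 in scenario B, type I error without centre is nominal within simulation error.

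**Strata are not covariates, so a statistical analysis plan could still add them.** This is a fair reason not to count the unstratified log-rank test as a fault, and it is not counted here. It is weaker for the Cox model: the protocol sets out that model's adjustment variables one by one, carries over the other two allocation factors, and says nothing of centre.

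**Neither scenario follows the protocol's calendar.** Also fair. Section "Research time" ends data collection in October 2028, so most patients would not reach 36 months. Suppose the yearly counts of 400, 600 and 400 mean uniform enrolment, with the stated medians and no dropout. About 549 events would then occur by the end of October 2028 and about 604 by the end of December 2028. That is nearer scenario B than A, so the power above 98% in scenario A should not be read as the trial's expected power.

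**Conclusion.** The point holds. The stated primary model omits one of the three factors on which allocation is balanced. If centres differ, the test is conservative and the hazard ratio is drawn toward 1. With a residual between-centre SD of 0.3 to 0.5 and 10 equal centres, the cost is 0.2 to 0.9 points of power over a full 36 months and 0.8 to 2.3 points at 508 events. It is zero if centres are alike. Direction and size are consistent across the layouts tried, but the size rests on assumed centre numbers and spread. Type I error is not inflated and no conclusion of the trial is put at risk. It is worth changing because the remedy is nearly free and because fixing it in advance prevents a later choice between results with and without centre.

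Separately, the bands 45-65 and 65-80 both contain age 65, in the minimisation and in the model. This is clerical and adds no weight to the main point.

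**What to change.** In section 10, stratify the primary Cox model by trial centre and keep age group, gender and the other listed variables as covariates. Before unblinding, fix a pooling rule for very small centres, for example centres with fewer than 20 patients combined in one stratum. Use the same strata for the supporting log-rank test. Define the age bands so that 65 falls in one band only, identically in the minimisation program and the model.

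This is one line of text, and centre is already known for every patient because the minimisation needs it. If centres are alike, stratifying costs at most about 0.1 point of power with 3 or 10 centres, equal or unequal.

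Many tiny centres are the awkward case. At 508 events and SD 0, keeping each as its own stratum costs 0.5 points (20 centres of 15 patients plus 10 of 110) or 1.0 point (50 centres of 6 plus 10 of 110). Pooling cuts these to 0.2 and 0.1 points. At SD 0.3/0.5 the pooled strata gain 0.4/1.7 points in the first layout and 0.5/1.8 in the second.

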(numerical range), reasonableness (whether the category is reasonable), and handling of missing data (by checking and supplementing missing data). Then conduct statistical analysis. Missing data will be compensated through multiple imputation and pattern mixing methods to explore the robustness of treatment effect estimation. We will explore the reasons for missing data, such as loss to follow-up or withdrawal, and report them. We will seek clarification of missing data through routine data collection with the clinical team. Resolve data queries before analysis.

11、 Ethics in Clinical Research

Clinical research will follow relevant regulations such as the Helsinki Declaration of the World Medical Assembly. The clinical study will only be conducted after the ethics committee approves the trial protocol before the start of the research. Before each participant is enrolled in this study, the researcher is responsible for fully and comprehensively introducing the purpose, procedures, and potential risks of this study to the participant or their representative, and signing a written informed consent form. The participant should be informed of their right to withdraw from this study at any time, and the informed consent form should be kept as a clinical research document for future reference. During the research process, the personal privacy and data confidentiality of the subjects will be protected.

Research time

January 2026 December 2026: Project initiation, completion of data

collection for 400 patients

January 2027 December 2027: Complete data collection and mid-term analysis for 600 patients

January 2028 to October 2028: Complete data collection for 400 patients

October 2028 to December 2028: Data organization and statistical analysis. Complete the paper writing and submit the SCI paper as soon as possible.

Reference

1. 蔡林, 朱称心, 张兴龙, 房怡, 杨海燕, 郭兰伟: 全球肺癌流行数据解读. 中华流行病学杂志 2024, 45(04):585-590.
3. Ben-Eliyahu S, Golan T: Harnessing the Perioperative Period to Improve Long-term Cancer Outcomes. JNCI: Journal of the National Cancer Institute 2018, 110(10):1137-1138.
4. Wall TP, Buggy DJ: Perioperative Intravenous Lidocaine and Metastatic Cancer Recurrence - A Narrative Review. Frontiers in Oncology 2021, 11.

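### The project calendar ends with an analysis in October-December 2028, before any patient can have reached the 36 months from surgery on which the primary outcome is defined

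*Protocol*

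**What the plan says.** **Outcome and follow-up.** Protocol section '6. Observation project' gives the main outcome as "Assess the reoccurrence time of lung cancer patients within 36 months from the date of surgery". Among the other indicators it lists "The total length of hospital stay, including readmission, is 36 months". Section '7. Efficacy evaluation criteria' schedules chest CT at 6, 12, 18, 24 and 36 months. Section '10. Statistics process' repeats the 36-month window. It lists as censored those free of recurrence or death at 36 months, those lost to follow-up and those withdrawn.

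**Calendar.** The 'Research time' section has four lines:

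- The first covers the calendar year 2026: the project begins and a first block of 400 is completed.
- The second covers 2027 and is worded "January 2027 December 2027: Complete data collection and mid-term analysis for 600 patients", so an interim look is placed in that year.
- The third covers the next ten months and is worded "January 2028 to October 2028: Complete data collection for 400 patients", which makes it the last block of patients.
- The fourth is worded "October 2028 to December 2028: Data organization and statistical analysis", and the paper is to be prepared and sent off in the same period.

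Nothing is listed after December 2028. The three blocks sum to 400 + 600 + 400 = 1400, which is the target in section 1.1: "Therefore, the planned total sample size is 1400 patients with lung cancer".

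**Sample size.** Section 1.1 assumes medians of 18 and 24 months, HR 0.75, 90% power and two-sided 0.05, and concludes: "Using PASS11 software, it is estimated that each group requires 635 cases". It states no accrual period and no follow-up period.

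**The concern.** The follow-up schedule and the calendar cannot both be carried out. The calendar is the only place in the protocol that dates the analysis and the publication. It puts a mid-term analysis in 2027, so the 2028 analysis reads as the concluding one.

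The blocks are described as data collection, which can be read in three ways. None gives a calendar that delivers the stated primary outcome:

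- **Recruitment.** No patient reaches 36 months by the last listed date.
- **Completed 36-month data.** The surgeries would have to precede the start of the trial.
- **Perioperative data only.** The calendar leaves out both the follow-up and the primary analysis.

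If the trial were analysed on these dates, the report would contain no 36-month CT and no 36-month hospital-stay data. The hazard ratio would describe mainly the first one to two years. Most patients would be censored for a reason that section 10 does not list, namely being event-free at a calendar cut-off before 36 months. Leaving the date open also allows the timing of the primary analysis to be chosen after data have accumulated.

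**Working it through.** **1. Date arithmetic (no accrual assumption).** The earliest possible surgery is 1 January 2026. Adding 36 months gives 1 January 2029, which is later than 31 December 2028. Patients with 36 months of follow-up: 0 of 1400. If the last surgery is in October 2028, the last 36-month CT falls in October 2031.

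**2. Follow-up at a 2028 cut.** Assume the blocks are recruitment with uniform entry within each. With month 0 = 1 January 2026, 400 patients enter over months 0-12, 600 over months 12-24 and 400 over months 24-34. Follow-up is cut-off minus entry, capped at 36 months.

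| | End Oct 2028 (month 34) | End Dec 2028 (month 36) | Full schedule |
|---|---|---|---|
| Patient-months | 22,800 | 25,600 | 50,400 |
| Mean follow-up (÷ 1400) | 16.3 | 18.3 | 36 |
| Reached 6 months | 1160 | 1240 | 1400 |
| Reached 12 months | 900 | 1000 | 1400 |
| Reached 18 months | 600 | 700 | 1400 |
| Reached 24 months | 333 | 400 | 1400 |
| Reached 36 months | 0 | 0 | 1400 |
| CTs due (sum of the five rows above) | 2,993 | 3,340 | 7,000 |
| Patient-months in year 3 | 1,667 | 2,400 | 16,800 |

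So 160-240 patients (11-17%) have not reached their first CT, 43-48% of scheduled CTs are due, and 10-14% of third-year follow-up exists.

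**3. Events needed.** Schoenfeld: 4 × (1.960 + 1.282)² / (ln 0.75)² = 508.

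**4. Events expected.** Use exponential times with the protocol's medians of 18 and 24 months, allocated 1:1. The event probability by time t is the average over arms of 1 − exp(−t × ln 2 / median). At t = 36 the arms give 0.75 and 0.646, mean 0.698, so 1400 × 0.698 ≈ 978 events, of which about 205 fall in year 3. Averaged over the entry pattern in step 2, the probability is 0.392 at month 34 and 0.431 at month 36. The 2028 cut therefore gives 549 to 604 events, of which 22 to 31 fall in year 3.

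**5. Power.** Power = Φ(√(events/4) × |ln 0.75| − 1.960).

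| Assumption at the 2028 cut | Events | Power |
|---|---|---|
| No dropout | 549-604 | 92-94% |
| 10% of patients contribute no events | 494-543 | 89-92% |
| Recurrence seen only at scheduled CTs | 452-500 | 86-90% |
| Both | 406-450 | 83-86% |

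The last three rows are sensitivity assumptions; the protocol does not state them.

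**6. The protocol's 635 per group.** It cannot be reproduced from what section 1.1 states, because the event probability is not given. It implies 508 / (2 × 635) = 0.40.

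- With 36 months for everyone: 508 / (2 × 0.698) = 364 per group.
- On the calendar blocks with a late-2028 cut: 508 / (2 × 0.392) = 648 down to 508 / (2 × 0.431) = 589.

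The figure 635 lies in the second range, so it may have been derived from the 2028 calendar. That is inference only.

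**The case against.** The strongest reply is that a time-to-event analysis does not need every patient to reach 36 months. Cox regression, Kaplan-Meier and log-rank methods accommodate administrative censoring, and 36 months can be an upper limit. The calendar never calls the 2028 work final or says that follow-up stops. On the protocol's medians without dropout, a late-2028 cut exceeds the 508 events needed. Under the constant hazards that section 1.1 assumes, an earlier cut does not bias the hazard ratio. Even with full follow-up, about 79% of events (773 of 978) fall in the first two years, against about 95-96% at the 2028 cut. A cut-off date is also often left to the SAP.

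Much of this stands:

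- A 2028 analysis would be valid as an early analysis, and a serious loss of power is not shown. The lowest power figures stack two assumptions. The CT-only one is harsh, because the section 10 model also counts deaths, which do not wait for a scan.
- The 36-month data would be missing from a 2028 report, not necessarily from the trial.

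The contradiction remains. The objection does not dispute the date arithmetic. The protocol describes no calendar cut-off, minimum follow-up or event target, and its list of censored patients has no place for one. A SAP can define a cut-off, but it cannot fit 36 months in before January 2029.

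**Conclusion.** The concern holds and must be fixed. On the protocol's own dates, 0 of 1400 patients can complete the 36-month window by the last listed analysis. That result rests on date arithmetic alone.

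The amount of follow-up lost depends on reading the blocks as recruitment with even entry: mean follow-up of 16.3-18.3 months instead of up to 36, and 22-31 of about 205 expected third-year events. Whether 90% power is met depends on which analysis is meant. It is met at a late-2028 cut without dropout (92-94%), not assured there once dropout or scan-based detection is allowed for, and comfortably met with full follow-up (about 978 events without dropout). The main defect is that the timing of the primary analysis is contradictory; a loss of power is possible but not established.

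**What to change.** Reconcile 'Research time' with sections 1.1, 6, 7 and 10, and state when the primary analysis takes place. There are two workable options:

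1. **Primary analysis after full follow-up.** Date it after the last patient's 36-month CT (about October 2031 if the last surgery is in October 2028), add the follow-up period to the calendar, and label any 2028 report as early results. The cost is a later final result and about three years beyond the stated calendar, which the CT schedule already requires.
2. **Primary analysis in 2028.** State a data cut-off date and a minimum follow-up or event target, add censoring at the cut-off to the list in section 10, and say that 36-month outcomes will be reported later. The 36-month limit can stay as the upper end of the window. For the primary analysis the cost is wording only, with the scheduled follow-up continuing for the later report.

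In either case, state in section 1.1 the accrual and follow-up periods behind 635 per group. Neither option needs more patients or procedures.
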